8.1 Study Design

This is a single arm, multi-center, phase II study evaluating the safety and efficacy of treating locally advanced and metastatic BCC patients with vismodegib alone followed by concurrent vismodegib with radiation therapy for a total of 21 weeks. After completing protocol therapy patients will be followed for 12 months. The primary efficacy study outcome measure is the proportion of patients with local-regional control at 12 months after completing protocol therapy.

8.2 Study Endpoints

Primary Endpoint:

- The proportion of patients with local-regional control at 12 months from protocol therapy completion, defined as complete or partial response, with absence of PD (see section 7.2) within the irradiated PTV.

Secondary Endpoints:

- Estimate of the probability of PFS and OS 12 months after protocol therapy completion. PFS is measured until disease recurrence or death due to any cause, whichever occurs first.
- Number and attribution of all adverse events (including vital signs, physical findings, and clinical laboratory results, CTCAE, v 4.0) in patients who receive any amount of study drug and radiation therapy.
- For each toxicity, the maximum occurring grade will be tabulated for each patient. The results will be summarized by toxicities observed during vismodegib treatment alone, during concurrent vismodegib with radiation therapy, for 3 months immediately following the completion of protocol therapy and for up to 12 months after completion of protocol therapy. The focus will be on the proportion of patients experiencing \geq grade 3 toxicity during each of these intervals.
- Proportion of patients experiencing Grade 4-5 adverse events assessed to be definitely, probably, or possibly related to the induction or concurrent treatment components of the protocol regimen (that is not definitely related to disease progression).
- Proportion of patients discontinuing treatment due to toxicity during the concurrent administration of vismodegib and radiation therapy. For this endpoint, discontinuation is defined as $<$ 75% of planned radiation therapy delivered.
- Response rate per RECIST criteria in patients who complete initial combined therapy of the primary site and regionally involved areas in subjects with measurable disease prior to initiation of therapy at 3 months after completion of protocol therapy.
- Proportion of patients with a decrease of BCC within the irradiated PTV after completing all protocol therapy to estimate clinical response to vismodegib and radiation therapy.

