2.2 Secondary

- To estimate of the probability of progression free survival (PFS), with failure defined as any disease recurrence or death due to any cause, and overall survival (OS) with the duration for each measured from the time of first treatment with vismodegib to 12 months after completion of study treatment.
- To evaluate toxicity during the drug-alone and combined-modality components of the protocol regimen during treatment. This will be assessed by

- The number and attribution of all adverse events, (including vital signs, physical findings, and clinical laboratory results, CTCAE, v 4.0) in patients who receive any amount of study drug and radiation therapy.
- The proportion of any adverse events (CTCAE, v. 4.0) assessed to be definitely, probably, or possibly related to vismodegib or its combination with radiation therapy.
- The proportion of patients experiencing Grade 4-5 adverse events assessed to be definitely, probably, or possibly related to the induction or concurrent treatment components of the protocol regimen (that is not definitely related to disease progression).
- To evaluate initial toxicity during the 3 months immediately after completion of protocol therapy.
- To estimate the feasibility of administering concurrent vismodegib with radiation therapy determined by the proportion of patients discontinuing treatment due to toxicity during the concurrent administration of vismodegib and radiation therapy (<75% of planned radiation therapy delivered)
- To evaluate the response rate (as per RECIST) at completion of protocol therapy of the primary site and regionally involved areas in subjects with measurable disease prior to initiation of therapy at 3 months after the completion of protocol therapy.
- To evaluate the clinical response to vismodegib and radiation therapy determined by the proportion of patients with a decrease of BCC within the irradiated planning tumor volumes (PTVs) in patients who complete the combined therapy.

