4.1 Description, Supply and Storage of Investigational Drugs

4.1.1 Vismodegib

Vismodegib capsules will be taken orally (whole). Patients receive vismodegib on an outpatient basis. Patients are instructed to swallow one capsule once a day (preferably at the same time each day) 7 days/week, with or without food, with about 1 cup (240 mL) of water. Capsules must be swallowed whole; they must not be opened, chewed, broken, or crushed under any circumstances. It is preferable that vismodegib be taken prior to radiation therapy throughout the treatment course. If a patient misses a dose (e.g., due to emesis), he or she should be instructed not to take or make up that dose and to resume dosing with the next scheduled dose. Missed doses will not be made up.

Patients will be asked to document daily vismodegib on a pill diary during pre-radiation treatment and concurrent treatment, which will be collected by the institution as source documentation. Institutions will submit a (DP) form at the end of both induction treatment and concurrent treatment.

Classification

Inhibitor of the hedgehog (Hh) signaling pathway

Mechanism of Action

Vismodegib is a more potent novel and specific synthetic oral hedgehog pathway inhibitor with an IC₅₀ of 3 nM. Vismodegib targets the Hedgehog signaling pathway, blocking the activities of the Hedgehog-ligand cell surface receptors PTCH and/or SMO and suppressing Hedgehog signaling. The Hedgehog signaling pathway plays an important role in tissue growth and repair; aberrant constitutive activation of Hedgehog pathway signaling and uncontrolled cellular proliferation may be associated with mutations in the Hedgehog-ligand cell surface receptors PTCH and SMO. Vismodegib also inhibits ABCG2, Pgp, and MRP1-important ABC transporters associated with multidrug resistance.

Metabolism

Greater than 98% of the total circulating drug-related components are the parent drug. Metabolic pathways of vismodegib in humans include oxidation, glucuronidation, and pyridine ring cleavage. The two most abundant oxidative metabolites recovered in feces are produced *in vitro* by recombinant CYP2C9 and CYP3A4/5.

Contraindications

None per product insert.

Availability

Each vismodegib capsule has a pink opaque body and a grey opaque cap with “150 mg” printed on the capsule body and “VISMO” printed on the capsule cap in black ink. Vismodegib capsules are available in bottles of 28 capsules (NDC 50242-140-01).

Storage and handling

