5.3 Dose Modifications and Dosing Delays

There are no planned dose reductions of vismodegib.

Treatment with vismodegib may be interrupted for up to 4 weeks for evaluation of an intolerable toxicity finding. In addition, treatment with vismodegib may be interrupted for up to 4 weeks if a patient becomes temporarily unable to swallow capsules or is in need of an unrelated surgical procedure which does not require disenrollment from the study. Any other proposed reasons for interruption of treatment should be discussed in advance with the Principal Investigator. If the patient resumes drug, administration will start at the point in the protocol at which was interrupted and the total durations of days of drug given to the patient should equal those specified in the protocol.

Radiation therapy should not be halted if at all possible and any radiation delays are to be stringently avoided, even if drug administration is interrupted. If radiation therapy treatments are interrupted for any reason, including holidays or mechanical breakdown, the missed treatments are to be added to the end of the treatment course, such that the total radiation dosage and days of radiation therapy given to the patient should equal those specified in the protocol.

If either vismodegib or radiation treatment has been held for more than 28 days to allow for resolution of an adverse event, the treating physician should contact the Study Chair to review the subject's condition prior to resuming the patient's treatment, except for delays due to hypertension. As a patient progresses from one treatment to another (i.e., pre-radiation therapy, radiation therapy, post radiation therapy), the patient should remain at the SAME DOSE LEVEL.

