8.4 Interim Analysis for Safety and Stopping Rules

An interim analysis for safety will be performed once 5 patients have been treated on study and completed all drug and radiation-based protocol therapy. This will occur approximately 7-8 months after the start of accrual assuming 2 patients are enrolled per month and protocol therapy is completed in about 5.5 months. After the fifth patient completes radiation therapy, accrual will be temporarily stopped in order to perform this interim analysis. Thus no additional patients will start radiation therapy during the evaluation interval that overlaps with the treatment period for patients included in the interim analysis. During the conduct of this study, toxicity will also be evaluated weekly so that any unacceptable toxicity can be identified early. If there is no reason to stop accrual (as defined below), the remainder of the 19 patients will be recruited.

Stopping rules: Acceptable occurrence of toxicity is defined as the discontinuation of treatment in $\leq 40\%$ of patients (2 of 5 patients who discontinue protocol treatment, having completed $< 75\%$ of planned radiation therapy) and the proportion of patients with grade 4-5 toxicity is $\leq 20\%$.

Accrual of the final 19 patients will be determined by the results of the interim analysis.

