The secondary clinical aims of the duration of progression free survival (PFS) and overall survival (OS) will be measured from the start of protocol therapy until death due to any cause or until the first evidence of any disease progression, or death, respectively. Point estimates (e.g. median, percent PFS at 12 months) with 95% confidence intervals will be calculated using the Kaplan-Meier product limit method to summarize results. Based upon RECIST criteria, the proportion of patients responding in the primary site and regionally involved areas at 3 months after completing protocol therapy will be determined and presented with 95% confidence intervals. The proportion of patients achieving any decrease in BCC within the boundaries of the treated radiation PTV area will be determined and presented with a 95% confidence interval. In addition, the proportion of patients who start concurrent vismodegib and radiation therapy and receive at least 75% of the planned radiation therapy will be determined and presented with a 95% confidence interval to summarize the feasibility of administering concomitant therapy.

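### The feasibility endpoint for concurrent vismodegib and radiation counts only radiation delivered, so a patient who stops the drug for toxicity but finishes radiation is a feasibility success

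*Combined protocol and SAP*

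**What the plan says.** - **Objective.** Section 2.2 sets out the aim: "To estimate the feasibility of administering concurrent vismodegib with radiation therapy determined by the proportion of patients discontinuing treatment due to toxicity" in the concurrent phase, with less than 75% of planned radiation as the criterion. The Abstract and Section 2.3.2 say the same.
- **Endpoint.** Section 8.2: "For this endpoint, discontinuation is defined as" less than 75% of planned radiation delivered. No vismodegib dose, duration or compliance criterion is given.
- **Analysis.** Section 8.5 lists the frequency of toxicity-related discontinuation in the concurrent phase among the safety summaries. It then adds a feasibility proportion: "the proportion of patients who start concurrent vismodegib and radiation therapy and receive at least 75% of the planned radiation therapy will be determined", with a 95% confidence interval and no target value.
- **Conduct.** Section 5.3 allows vismodegib to be interrupted for up to 4 weeks, and says of radiation that "any radiation delays are to be stringently avoided, even if drug administration is interrupted". Section 5.3.1 describes stopping vismodegib for new, related grade 3 or 4 events that meet its further conditions.
- **Interim rule.** Section 8.4 has two limits. Discontinuation is acceptable in at most 40% ("2 of 5 patients who discontinue protocol treatment, having completed" less than 75% of planned radiation), and grade 4-5 toxicity in at most 20%. Weekly toxicity evaluation is added without a numeric limit.
- **Data.** Section 4.1.1: "Patients will be asked to document daily vismodegib on a pill diary during pre-radiation treatment and concurrent treatment". Section 5.1 has the diaries returned about every four weeks.

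**The concern.** The objective asks whether two treatments can be given together. The endpoint looks at one of them, and it is the one that the protocol protects: sites are told to keep radiation going when the drug is held. Intolerance of vismodegib during radiation will therefore tend to appear as missed drug, not as missed radiation, and no planned feasibility summary counts missed drug.

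At stake is the reading of the result. A high proportion would be taken as evidence that the combination is deliverable, and would inform any later trial of it. The same figure could arise if a substantial share of patients had most of their radiation without the drug. A smaller, related matter is that one of the two interim limits uses the same definition.

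**Working it through.** **1. The plan's own figure.** The only stated power is for the primary endpoint (Section 8.3.1): n = 24, null 60%, alternative 80%, one-sided 0.10, exact binomial. The smallest cut-off r with P(X ≥ r | 24, 0.60) ≤ 0.10 is r = 18 (0.0960; r = 17 gives 0.192). Power is P(X ≥ 18 | 24, 0.80) = 0.811, which agrees with the stated 81%. Feasibility has no target or power, so nothing below alters this.

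**2. How the definition sorts patients who start concurrent treatment.**

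| Radiation received | Vismodegib | Classified as | Combination given as planned? |
|---|---|---|---|
| ≥75% | taken as planned | feasible | yes |
| ≥75% | stopped or long held for toxicity | feasible | no |
| <75% | either | not feasible | no |

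The second row is the gap. Sections 5.3 and 5.3.1 both foresee it.

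**3. Size for one patient.** Planned concurrent doses: 7 weeks × 7 days = 49. A 28-day interruption leaves 49 − 28 = 21, and 21/49 = 43%. Counting only from first to last fraction at five per week, 33 fractions span 45 days and 35 span 47. What is left is then 17/45 = 38% or 19/47 = 40%. Section 5.3 also asks that drug days be made up after an interruption, but days taken after radiation ends are not concurrent. The classification stays feasible throughout.

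**4. Size for the reported proportion.** The documents give no rate of drug stops, so this is an illustration. Assume 24 patients start concurrent treatment, all reach 75% of radiation, and 8 or 12 stop vismodegib for toxicity (exact 95% intervals).

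| | Plan's figure | Both components met |
|---|---|---|
| 8 stop the drug | 24/24 = 100% (85.8 to 100) | 16/24 = 66.7% (44.7 to 84.4) |
| 12 stop the drug | 24/24 = 100% (85.8 to 100) | 12/24 = 50.0% (29.1 to 70.9) |

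**5. Interim rule, 5 patients.** The discontinuation limit is exceeded at 3 or more of 5, and the grade 4-5 limit at 2 or more of 5. Let a be the probability of a radiation stop, d that of a drug-only stop for toxicity, and f the share of drug-only stops that are grade 4-5. Assume a = 5% and no other grade 4-5 events. The discontinuation limit alone is exceeded with probability P(X ≥ 3 | 5, 0.05) = 0.1%, whatever d is. For the whole rule (exact multinomial), the first figure in each cell is the rule as written. The second is what it would be if drug stops also counted toward the discontinuation limit.

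| d | f = 0 | f = 0.5 | f = 1 |
|---|---|---|---|
| 20% | 0.1% / 10.4% | 8.3% / 14.6% | 26.4% / 27.2% |
| 30% | 0.1% / 23.5% | 16.6% / 29.7% | 47.3% / 48.2% |
| 40% | 0.1% / 40.7% | 26.4% / 47.3% | 66.4% / 67.3% |
| 50% | 0.1% / 59.3% | 36.8% / 65.0% | 81.3% / 82.1% |

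As a check on the f = 0 column, at d = 20% the second figure is P(X ≥ 3 | 5, 0.25) = 10.4%. In the extreme case, if all 5 stop vismodegib for grade 3 toxicity and finish radiation, feasibility is 5/5 and neither limit is exceeded. If 2 of the 5 events are grade 4, the second limit is.

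**The case against.** The best reply is that this is one missing summary for an untested secondary endpoint. Drug intake is captured in diaries and treatment forms (Sections 4.1.1 and 5.1, Appendix 8), compliance is scored for every patient (Section 9.7), and grade 3 or higher toxicity is summarised separately for the concurrent interval (Section 8.2). Section 5.3.1 is also narrow: a grade 3 event must be likely to be life-threatening or irreversible, so required drug stops may be few. All of this is true, and it keeps the point modest. But a toxicity table does not show whether the drug was stopped, and collecting diaries does not commit anyone to report them.

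Some stronger readings are tempting and do not hold:

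- *The stopping rule cannot see drug intolerance.* The grade 4-5 limit sees it when the toxicity is of that grade. In the f = 1 column the rule as written performs almost the same as one that counts drug stops. Weekly evaluation and committee review could notice other cases.
- *Section 8.5 abandons toxicity as the reason for stopping.* It keeps the toxicity-related frequency and presents the any-reason proportion as an addition. Both are planned; both rest on radiation.
- *A patient could take no concurrent drug and count as feasible.* The denominator in Section 8.5 is patients who start concurrent vismodegib and radiation. Gaps beyond 28 days also meet the Study Chair review in Section 5.3 and the withdrawal ground in Section 6.1.6.
- *The endpoint would always show no discontinuation, and the interim limit would never be reached.* That holds only if nobody stops radiation early, which the documents do not say.

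**Conclusion.** The point holds for the feasibility endpoint. As defined in Sections 2.2, 2.3.2, 8.2 and 8.5 it measures radiation completion, and a patient with about 38% to 43% of planned concurrent doses, after an interruption that the protocol permits, is a success. This follows from the text and needs no assumed event rate. How far the reported proportion would overstate deliverability depends on the rate of drug-only stops, which the documents do not give. The 100% against 50% to 67% contrast is an illustration, not a forecast.

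For the interim rule the conclusion is narrower. The discontinuation limit does not respond to drug stops, and the rule as a whole misses them when the toxicity is below grade 4. Whether that limit should count drug stops is a safety decision for the sponsor. The documents leave it unclear and do not show that the present limit is wrong.

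The primary endpoint, sample size and power are untouched. The change should be made, because a named objective is otherwise not answered by its own endpoint.

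**What to change.** In Sections 8.2 and 8.5, keep the radiation criterion and add a vismodegib component from the pill diaries. Among patients who start concurrent treatment, report with 95% confidence intervals where a proportion is given:

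1. the proportion who stop vismodegib for toxicity during radiation;
2. the proportion of planned concurrent doses taken, per patient and summarised;
3. the joint proportion meeting both the 75% radiation criterion and a drug criterion that the sponsor fixes in advance. A cut-off of 75% would mirror the radiation one, but nothing in the documents dictates it.

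Show drug-only, radiation-only and joint discontinuation separately, and say how doses made up after radiation are treated.

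Separately, ask the sponsor to reconcile these passages:

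- Section 5.3 continues radiation when the drug is interrupted, Section 5.3.1 foresees stopping the drug, and Section 6.1.6 lists adverse events and delays over 4 weeks as withdrawal grounds. None says whether a permanent drug stop ends protocol radiation.
- Section 5.3 asks for drug days to be made up, while Section 4.1.1 says missed doses are not.
- Section 8.4 describes the 5 interim patients as having completed both treatments, yet counts discontinuations among them. It should state whether drug stops count toward that limit.

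The cost of the endpoint change is a little more analysis and possibly a less favourable feasibility figure. N = 24 and the 81% power stay as they are. Counting drug stops in Section 8.4 would not be free: with 5% radiation stops and no grade 4-5 events, the chance of exceeding a limit at a 40% drug-stop rate goes from 0.1% to 40.7%. Operating characteristics should be set out before any such choice.

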2.3.2 Secondary Endpoints

- Estimate of the probability of PFS, with failure defined as any disease recurrence or death due to any cause, and OS with each duration measured from the time of first treatment with vismodegib to 12 months after completion of study treatment.
- The number and attribution of all adverse events, (including vital signs, physical findings, and clinical laboratory results, CTCAE, v 4.0) in patients who receive any amount of study drug and radiation therapy at any point during protocol therapy or during the followup period.
- The proportion of any adverse events (CTCAE, v. 4.0) assessed to be definitely, probably, or possibly related to vismodegib or its combination with radiation therapy at any point during protocol therapy or during the followup period.
- The proportion of patients experiencing Grade 4-5 adverse events assessed to be definitely, probably, or possibly related to the induction or concurrent treatment components of the protocol regimen (that is not definitely related to disease progression) at any point during protocol therapy or during the followup period.
- The proportion of patients discontinuing treatment due to toxicity during the concurrent administration of vismodegib and radiation therapy (<75% of planned radiation therapy delivered).
- Response rate (as per RECIST) of the primary site and regionally involved areas following all treatment components at 3 months after the completion of protocol therapy.

- Proportion of patients with a decrease of BCC within the irradiated planning tumor volumes (PTV) in patients who complete initial combined therapy, indicating a clinical response to vismodegib and radiation therapy.

3 Study Design

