8.5.1 Analysis Population

The statistical analysis of efficacy will include all patients completing the initial treatment with vismodegib alone and start the concurrent vismodegib with radiation therapy. Anyone who receives any vismodegib with radiation therapy will be included in the assessment of efficacy. As the most conservative approach, any patient removed from study prior to completion of at least 75% of radiation therapy without a documented complete or partial response will be considered as a case of local-regional failure.

Failure is defined as a lack of local-regional control within the boundaries of the treated radiation PTV area within the 12 month follow-up period.

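### Two secondary efficacy rates, 3-month RECIST response and tumour decrease within the PTV, have conflicting denominators: completers in some sections, all starters of concurrent therapy in others

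*Combined protocol and SAP*

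**What the plan says.** **3-month RECIST response.** Section 8.2 defines it as "Response rate per RECIST criteria in patients who complete initial combined therapy", further limited to patients with measurable disease before treatment. No other statement of this endpoint carries the completer restriction. Section 2.3.2 has "Response rate (as per RECIST) of the primary site and regionally involved areas following all treatment components at 3 months", where the treatment phrase can be read as timing. The Abstract and 2.2 have no completer clause for this endpoint, and 8.5 reports "the proportion of patients responding in the primary site and regionally involved areas at 3 months" without one.

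**Tumour decrease within the PTV.** Here the pattern reverses. Section 2.2 gives the "proportion of patients with a decrease of BCC within the irradiated planning tumor volumes (PTVs) in patients who complete the combined therapy". Section 2.3.2 limits it to results "in patients who complete initial combined therapy, indicating a clinical response to vismodegib and radiation therapy", and the Abstract also limits it to completers. Section 8.2 reads "Proportion of patients with a decrease of BCC within the irradiated PTV after completing all protocol therapy", which may describe when the decrease is assessed rather than who is counted. Section 8.5 has no restriction.

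**Populations.** Section 8.5.1 defines the efficacy population as patients who finish induction and start concurrent treatment, and adds: "Anyone who receives any vismodegib with radiation therapy will be included in the assessment of efficacy". It makes no exception for secondary endpoints. Patients removed before 75% of radiotherapy count as local-regional failures unless a complete or partial response was documented. Section 7.2.1.1 defines a different set as evaluable for response: measurable disease, at least 75% of radiotherapy and a re-evaluation, plus patients who progress during induction. The documents do not say whether completing combined therapy means the full course or at least 75% of radiotherapy.

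**The concern.** Completing combined therapy is known only after treatment has begun. Sections 3.4 and 6.1.6 list disease progression and adverse events among the reasons for stopping. Patients who progress during radiotherapy therefore drop out of a completers-only denominator, and they are poor-outcome patients. A rate computed that way describes a subset selected by how treatment went. It cannot be set beside the primary result, which 8.5.1 bases on everyone who starts concurrent therapy.

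The conflict also leaves the choice of denominator open at the time of analysis. An analyst following 8.2 for response, or 2.2 and 2.3.2 for decrease, could report a different figure from one following 8.5 and 8.5.1, and each could cite the plan. Both rates will be read as supporting evidence of activity.

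**Working it through.** **The plan's own figure.** The only related figure in the plan is the power of the primary test (8.3.1): n = 24, p0 = 0.60, p1 = 0.80, directional alpha 0.10, exact binomial.

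- P(X ≥ 17 | 0.60) = 0.192, which exceeds 0.10. P(X ≥ 18 | 0.60) = 0.0960, so the test rejects at 18 or more of 24.
- Power = P(X ≥ 18 | 0.80) = 0.811.

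This reproduces the stated 81%. It concerns local-regional control at 12 months and does not depend on the two secondary denominators.

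**Inputs for the secondary rates.**

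- Completers: 24, the evaluable number in 3.2 and 8.3.1.
- Responders among completers: 20, an assumption, so pc = 20/24 = 0.833.
- Early stoppers m: 2, 4 or 6, an assumption; the documents give no expected number.
- Response rate q among stoppers: also an assumption. The values are 0; 0.43 and 0.60 (vismodegib alone in locally advanced BCC by independent review and by investigators, 1.2.2); and pc.

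**Formula.** All-starters rate = (24·pc + m·q)/(24 + m). Gap = completers' rate − all-starters rate = [m/(24 + m)]·(pc − q).

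With q = 0 the all-starters rates are 20/26 = 76.9%, 20/28 = 71.4% and 20/30 = 66.7%, against 83.3%. Worked example for m = 4 and q = 0.43: (4/28) × (0.833 − 0.43) = 0.058.

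| m | q = 0 | q = 0.43 | q = 0.60 | q = pc |
|---|---|---|---|---|
| 2 | 6.4 | 3.1 | 1.8 | 0 |
| 4 | 11.9 | 5.8 | 3.3 | 0 |
| 6 | 16.7 | 8.1 | 4.7 | 0 |

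Gaps are in percentage points.

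**Stoppers who are not replaced.** Under 8.3.2, a patient who stops before 75% of radiotherapy with grade 3 or higher toxicity is not replaced, so some stoppers may fall inside the 24. With 24 starters, an assumed completer rate of 80% and m non-completers, the gap is (m/24)·(0.80 − q):

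| m of 24 | q = 0 | q = 0.43 | q = 0.60 | q = 0.80 |
|---|---|---|---|---|
| 1 | 3.3 | 1.5 | 0.8 | 0 |
| 3 | 10.0 | 4.6 | 2.5 | 0 |
| 6 | 20.0 | 9.3 | 5.0 | 0 |

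**The third set can move the other way.** Suppose 20 of 24 completers respond, nobody stops during radiotherapy, and 2 patients progress during induction. The 7.2.1.1 set gives 20/26 = 76.9%. The 8.5.1 set excludes those two and gives 20/24 = 83.3%. So the all-starters set is not the stricter one in every case.

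**The case against.** The strongest reply is that these are descriptive secondary estimates with no hypothesis test, and that attrition is already visible. Section 8.5 reports, with a 95% interval, the proportion of concurrent-therapy starters who receive at least 75% of radiotherapy. Section 8.2 reports discontinuation for toxicity, and 8.3.2 requires the frequency of replacements and the reasons for them. The primary analysis already uses all starters with a conservative failure rule. All of this stands and limits the consequence. It does not tell the analyst which denominator to use.

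It can also be argued that a specific endpoint definition overrides a general population statement. That does not settle the matter here, because the specific definitions disagree with each other: 8.2 against 2.3.2 for response, and 2.2 and 2.3.2 against 8.5 for decrease.

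A reader might infer that both rates are certainly inflated. The documents do not support that. Inflation requires stoppers to do worse than completers. Every patient who starts radiotherapy has had about 12 weeks of vismodegib (5.1), so a stopper may already have a documented response, and more easily some decrease. Section 8.5.1 allows for this by not automatically failing a stopper with a documented response.

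A reader might also infer that the plan consistently adopts a completers-only design for both endpoints. It does not: only 8.2 restricts the response rate, and 8.2's wording for decrease may be about timing.

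**Conclusion.** The denominators of the two rates conflict across the Abstract, 2.2, 2.3.2, 7.2.1.1, 8.2, 8.5 and 8.5.1, and should be reconciled. Upward bias from a completers-only denominator is the likely direction, but it is not established.

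Its size cannot be fixed from the documents, which give neither a non-completion rate nor a response rate among stoppers. In the main illustration (20 of 24 completers responding; 2, 4 or 6 stoppers) the gap runs from zero to 16.7 points. The top of that range assumes that no stopper responds. At 43–60% response among stoppers it is 1.8 to 8.1 points. Those two rates come from patients treated until progression or intolerable toxicity and serve only as illustrations. The effect on the tumour-decrease rate may be smaller. Non-completion need not be rare: the interim rule in 8.4 accepts discontinuation in 2 of 5 patients.

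The primary endpoint, alpha, sample size and power are unaffected. The change should be made, but the trial's main conclusion does not depend on it.

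**What to change.** Use one denominator for both rates in the Abstract, 2.2, 2.3.2, 7.2.1.1, 8.2 and 8.5:

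- **Population.** The 8.5.1 population: all patients who start concurrent vismodegib and radiotherapy, including those replaced under 8.3.2 after starting radiotherapy. For the RECIST rate, also require measurable disease at baseline.
- **Missing assessments.** Count a patient with no 3-month assessment as a non-responder unless a complete or partial response (for the second endpoint, a decrease) was already documented. This extends the principle of 8.5.1, whose own rule covers only local-regional failure, so it has to be written out. The text should also state the date from which the 3 months run for a patient who stops early.
- **Supplement.** Report the rate among completers, or among patients evaluable under 7.2.1.1, as a labelled supplementary figure, with completion defined.

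Section 7.2.1.1 and the Abstract must be changed with the rest; otherwise they would contradict the amended text. The cost is wording, one extra table line, and possibly slightly less favourable reported rates.
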